9.3	CASE REPORT FORMS	22
9.4	RECORDS RETENTION	23
10	STUDY MONITORING, AUDITING, AND INSPECTING	23
10.1	STUDY MONITORING PLAN	23
10.2	AUDITING AND INSPECTING	383
11	ETHICAL CONSIDERATIONS	38
12	STUDY FINANCES	394
12.1	FUNDING SOURCE	394
13	PUBLICATION PLAN	394
14	REFERENCES	24
15	ATTACHMENTS	26 ERROR! BOOKMARK NOT DEFINED.

LIST OF ABBREVIATIONS

AE	Adverse Event/Adverse Experience
CFR	Code of Federal Regulations
CRF	Case Report Form
DSMB	Data and Safety Monitoring Board
FDA	Food and Drug Administration
GCP	Good Clinical Practice
HIPAA	Health Insurance Portability and Accountability Act
ICU	Intensive Care Unit
IDE	Investigational Device Exemption
IRB	Institutional Review Board
NS	Nanopore Sequencing
PHI	Protected Health Information
PI	Principal Investigator
SAE	Serious Adverse Event/Serious Adverse Experience
SOP	Standard Operating Procedure
SSI	Surgical Site Infection
TRAG	Tissue Request Acquisition Group
UADE	Unanticipated Adverse Device Effect

Study Summary

Title	“Answers in Hours” A Randomized Controlled Trial Using Microbiome Metagenomics for Bile Duct Cultures
Running Title	“Answers in Hours”
IRB Protocol Number	21-004234
Phase	Pilot
Methodology	Randomized 1:1 Controlled Trial
Overall Study Duration	3 years
Subject Participation Duration	90 days
Objectives	
Reduce the rate of bacterobilia driven surgical site infection (SSI) in patients undergoing pancreatic head resection by providing surgical team with Oxford Nanopore (ONT) microbial sequencing data in the post-operative setting.
 
Reduce cost of care through reduction in SSI and improved antibiotic stewardship.

Number of Subjects	140
Diagnosis and Main Inclusion Criteria	Any adult, male or female, over age 18, undergoing pancreaticoduodenectomy or total pancreatectomy for benign or malignant indication.
Study Device	GridION Sequencing Instrument
Reference therapy	Standard culture techniques and prolonged peri-operative antibiotics
Statistical Methodology	For continuous variables, t-test will be performed and for binary variables chi-square or fisher's exact testing will be performed as appropriate. Universal and multivariable linear regression adjustment will be performed if any baseline imbalances in demographic or clinical variables are detected

1 Introduction

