2.2 Primary Objective

To improve antibiotic stewardship (reducing duration of peri-operative prophylactic antibiotic regimen, reducing administration of broad-spectrum antibiotic) by providing surgical team with rapid ONT sequencing data in the early post-operative setting.

Success Criteria: Significantly reduced antibiotic regimen duration and use of broad-spectrum antibiotics, corrected for key co-variates ($p<0.1$).

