2.1 General Design

This will be a prospective 1:1 randomized controlled trial with the following study arms:

Arm 1: Patient Group 1

Standard Care Only. Patients will undergo intra-operative bile aspiration (as is routinely performed) with SC of the aspirate. All patients will receive standard prophylactic antibiotics according to practice standards and will be continued for up to 5 days as is routine. If bile cultures are positive, antimicrobials will be continued for a complete 10-day course of antibiotics (Figure 2).

Arm 2: Patient Group 2

Standard Care + ONT. Patients will undergo intra-operative bile aspiration (as is routinely performed) with standard cultures AND ONT sequencing of the aspirate. All patients will receive standard prophylactic antibiotics according to practice standards. ONT sequencing results will be made available to providers through electronic medical record (EMR) and team electronic notifications. Patients with negative ONT results will be taken off the standard prophylactic antibiotics and patients with positive ONT results will have antimicrobial therapy adjusted according to ONT sequencing results. However, if SCs are positive or suggest alternative/broader coverage then these results

will guide therapy and not ONT results. If bile cultures are positive, antimicrobials will be continued for a complete 10-day course of antibiotics (Figure 2).

[figure not shown]

Figure 2: A schematic diagram of our proposed study to investigate the use of Oxford nanopore sequencing to detect and characterize biliary microbial contamination

The study will include patients undergoing elective pancreaticoduodenectomy or total pancreatectomy for any clinical indication. Patients will be excluded from the study if they are < 18 years of age, enrolled in any similar clinical trials involving use of peri-operative antibiotics, are undergoing distal pancreatectomy, or undergoing emergency total pancreatectomy or emergency pancreaticoduodenectomy (Table 4). Following recruitment to the study, patients will be randomly assigned intraoperatively/post-operative to either the control group (Arm 1) or the interventional group (Arm 2). We will use stratified randomization with age (below 65 years vs 65 years and above), sex, operation type (pancreaticoduodenectomy vs total pancreatectomy), biliary stenting (yes vs no), and patient ASA score as stratification factors.

Table 4: Patient inclusion and exclusion criteria for the clinical trial

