4.2 Method for Assigning Subjects to Treatment Groups

Two potential confounding variables exist in this patient population: operation type (pancreaticoduodenectomy vs total pancreatectomy) and pre-operative biliary stenting. Therefore, to eliminate potential bias between arms, patients will be stratified according to operation type (pancreaticoduodenectomy/total pancreatectomy) and biliary stenting (Y/N). Stratified patients will be assigned to arms by the study team using Medidata Rave with pre-determined assignments.

Given the prospective nature of this study, it will include subjects previously diagnosed with a specific disease and add newly diagnosed subjects in the future as patients are accrued.

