5.2 Sample Collection Visit

Following enrollment procedures, 2 cc of residual bile collected during surgery will be aliquoted into cryovial and placed on ice (not frozen). It will be picked up by the study team at the time of collection for ONT sequencing. Tissue Request Acquisition Group (TRAG) approval will be requested for managing of samples. The sample will be aliquoted from the clinical collection and so collection will not add additional time to the surgery procedure. Participants will be randomized in Medidata Rave to a study arm based on operation type and pre-operative biliary stenting using a dynamic stratification. Participants will be randomized in a 1:1 ratio.

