6.1 Sample Size Determination

Data for power analysis based on pilot study data (IRB# 19-011419). Power analysis is based on improvement in antibiotic stewardship with the following assumptions:

- Treatment groups are random and independent
- Microbial detection positivity rate using standard cultures = 54%
- Microbial detection positivity rate using nanopore sequencing = 77%

Analytical method:

- Sample size per group = 66 (total N = 132), Target size=70 per arm, total N=140
- Power = 80%, alpha (type I error) = 0.05, beta (type II error) = 0.2

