6.2 Statistical Methods

Descriptive Statistics

The primary analysis of this study will be a modified intention to treat analysis (ITT), performed to determine how use of ONT changed patient treatment, i.e. did use of ONT improve antibiotic stewardship. Proportions of patients with detection of microbes of interest will be estimated along with exact 95% binomial confidence intervals. Comparisons of the proportions between the two study arms will be compared using Fisher's exact test or Chi-square test as appropriate. We will calculate the time from randomization to first microbial detection within a patient. We will report the mean difference in time to first microbial detection within 96 hours post randomization in both treatment arms, together with a 95% confidence interval. Comparison of time to first microbial detection within 96 hours post randomization, will be performed using Wilcoxon rank sum test or two sample t-test as appropriate. If there are any baseline imbalances in demographic or clinical variables between the two groups, we will perform the analysis using univariable and multivariable linear regression adjusting for these variables with imbalances as possible confounders. Duration of antibiotics, total number of different antibiotics, and broad-spectrum antibiotics vs narrow-spectrum antibiotics administered in the two arms will be compared to determine if use of ONT improved antibiotic stewardship by significantly reducing the duration of perioperative antibiotics and use of broad-spectrum antibiotics

Secondary analysis will evaluate SSI's will be evaluated and classified using ACS NSQIP definitions and data collected will include mortality rate, SSI incidence rate, ICU length of stay, total length of hospital stay, need for interventional procedures, and hospital readmission. Statistical analysis will be performed by the study team to determine if use of ONT significantly improved patient outcome compared to patients who received standard of care

only. The secondary endpoint of the study is a binary endpoint i.e. whether patients develop SSI (yes, no). Association between the secondary outcome and predictor variables will be assessed using univariable and multivariable logistic regression.

In both primary and secondary analysis, the following variables will be assessed for inclusion in the regression models

- Age at time of surgery DOB
- BMI at time of surgery RAVE calculate
- Sex

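### The primary antibiotic-duration comparison has three poorly joined adjustment rules, and none commits the stratification factors to the model

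*Combined protocol and SAP*

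**What the plan says.** Section 5.3 makes duration of the perioperative antibiotic regimen a primary endpoint. Three rules bear on adjusting it.

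- **Default plus trigger.** The Study Summary names a t-test for continuous variables and adds: "Universal and multivariable linear regression adjustment will be performed if any baseline imbalances in demographic or clinical variables are detected". Section 6.2 repeats the trigger ("If there are any baseline imbalances in demographic or clinical variables between the two groups, we will perform the analysis") and, later, the t-test. Imbalance is not defined.
- **Screen.** Section 6.2 states: "In both primary and secondary analysis, the following variables will be assessed for inclusion in the regression models". Fifteen variables follow, with p<0.15 making a variable a candidate for the multivariable model. The list has stent, age, sex and ASA score. It omits operation type and includes post-operative TPN.
- **Success criterion.** Section 2.2 Primary Objective requires: "Significantly reduced antibiotic regimen duration and use of broad-spectrum antibiotics, corrected for key co-variates", at p<0.1. No covariate is named.

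Section 6.2's own sentence on duration says only that the arms will be compared. It gives no test or model.

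The stratification factors also differ between sections. Section 2.1 General Design says "We will use stratified randomization with age (below 65 years vs 65 years and above), sex, operation type", then adds stenting and ASA score, which makes five. Sections 4.2 and 5.2 have two; Section 5.2 randomises "based on operation type and pre-operative biliary stenting using a dynamic stratification".

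**The concern.** Stratifying on a prognostic factor makes the treatment estimate more precise, but the reported standard error shows this only if the factor is in the analysis. Stent is likely to be strongly prognostic for duration. In the pilot (Section 1.4, Table 1), 22 of 22 patients with biliary instrumentation had biliary microbes, against 1 of 20 without. Sections 1.1 and 2.1 tie the 5-day or 10-day course to the culture result. An analysis without stent therefore discards precision that the design has already obtained.

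The screen fails differently. It would usually admit stent, but it lets outcome data choose the model. It also allows adjustment for post-operative TPN, which arises after randomisation and could be affected by the arm. The trial is open-label (Section 4.3) and the study team does the analysis (Section 6.2), so it matters that one rule is fixed beforehand.

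**Working it through.** **The plan's own figure.** Section 6.1 compares detection rates of 54% and 77% with "alpha (type I error) = 0.05" and 80% power. With pooled variance, two-sided:

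n = [1.960·√(2·0.655·0.345) + 0.842·√(0.54·0.46 + 0.77·0.23)]² / 0.23² = (1.318 + 0.549)² / 0.0529 = 65.9, so 66 per group.

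The stated 66 reproduces, but it concerns detection, not duration. It gives no duration SD and no planned adjustment, so it cannot show which rule was meant.

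**Inputs from the documents.** 70 per arm; P(stent) = 22/42, using instrumentation as a proxy; durations of 10 days (culture-positive), 5 days (culture-negative) and 24 hours (negative ONT).

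**Assumed.** Patient SD of 2 or 4 days; full adherence; culture-positive Arm 2 patients at 10 days, as in Section 2.1 (Table 5 treats discordant results differently, and the two need reconciling); blocks of 4 within stent by operation strata.

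**Hand check.** Pilot link (100% and 5% culture-positive), SD 2, all culture-negatives ONT-negative:

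- P(culture-positive) = 0.524·1 + 0.476·0.05 = 0.548. Effect = 4·0.452 = 1.81 days.
- Total variance: control 25·0.548·0.452 + 4 = 10.19; ONT arm 81·0.548·0.452 + 4 = 24.07. Unadjusted SE = √(34.26/70) = 0.700.
- Within-stent variance: 25·0.0226 + 4 = 4.57 and 81·0.0226 + 4 = 5.83, where 0.0226 = 0.476·0.05·0.95. The stratum effects (0 and 3.8 days) differ, adding 3.8²·0.524·0.476/140 = 0.026. True SD of the estimate = √(10.40/70 + 0.026) = 0.417.
- Power at 0.05: unadjusted Φ[(1.81 − 1.977·0.700)/0.417] = 85%; stent-adjusted Φ[(1.81 − 1.977·0.417)/0.417] = 99%.

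**Simulation** (6,000 trials per setting; 4,000 at 85/25). Power, t-test against arm plus stent with robust SE:

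| Culture-positive, stent / no stent | SD | At 0.05 | At 0.10 |
|---|---|---|---|
| 100% / 5% (pilot) | 2 | 84.3 vs 98.6 | 93.6 vs 99.4 |
| 100% / 5% | 4 | 50.9 vs 70.1 | 65.9 vs 80.2 |
| 85% / 15% | 2 | 82.7 vs 92.7 | 91.4 vs 96.0 |
| 85% / 15% | 4 | 55.7 vs 64.9 | 69.1 vs 74.9 |
| 85% / 25% | 2 | 72.8 vs 82.5 | 84.0 vs 89.2 |
| 85% / 25% | 4 | 47.7 vs 53.5 | 60.8 vs 66.6 |
| 70% / 35% (weak) | 2 | 75.6 vs 78.4 | 85.3 vs 86.9 |
| 70% / 35% | 4 | 52.8 vs 55.0 | 66.0 vs 67.5 |

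The 85/25 rows lie near the inner exact 95% limits of the pilot rates (84.6% and 24.9%). Gaps run from 2.2 to 19.2 points at 0.05 and from 1.5 to 14.3 at 0.10. Under the null (pilot link, SD 2, alpha 0.05) the t-test rejects in 0.4% of trials and the adjusted model in 5.2%.

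**If fewer culture-negatives stop early.** Section 6.1's rates, with ONT detecting every culture-positive case (Section 1.4), leave 23% of patients ONT-negative among the 46% who are culture-negative, so half. If the other half stay at 5 days, the effect is 4·0.452·0.5 = 0.9 days. Power at 0.05 is then about 19% vs 59% (pilot link, SD 2), 24% vs 35% (85/25, SD 2) and 19% vs 20% (70/35, SD 4).

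**The screen.** It selected stent in 100% of runs at 85/25 or stronger, and in 98% (SD 2) and 90% (SD 4) at 70/35. In a separate simulation with assumed covariate strength, its own type I error stayed near 5%. Taking the smallest p over four analyses (t-test, fixed factors, trigger, screen) gave about 7%.

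**Operation type.** In the pilot, 18/33 against 5/9 had biliary microbes (Table 1, P = 0.9716). Adding it to the stent-adjusted model changed power by at most 0.2 points.

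**The case against.** The strongest reply is that the deciding analysis will be adjusted anyway. The Primary Objective requires correction for covariates, and Section 6.2 applies a list containing stent to the primary analysis. On that reading the power loss largely disappears. This stands, and it is why the loss is conditional. It does not rescue the plan: the covariates remain unnamed, the list omits a stratification factor, and the data choose the model.

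The text can also be read more narrowly. The trigger sentence follows the time-to-detection comparison, and the p<0.15 sentence leads into odds ratios and ROC curves, which suit SSI. But the Study Summary states the trigger generally, and Section 6.2 extends the list to the primary analysis in words.

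Some stronger readings are tempting but unsupported:

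- A reader might count four rules. The Study Summary gives the t-test and the trigger together, as default and exception, so three is fairer.
- A reader might infer more false positives from the t-test. The opposite holds: it is conservative.
- A reader might infer that the trigger can never admit stent. The plan gives no threshold. At an assumed p<0.05, stent imbalance occurred in 0 of 82,500 simulated trials. Yet stent proportions differed at least slightly in about 72% of two-factor trials, and by over 5 points in about 24% when five factors were assumed. Whether stent enters is undefined.
- A reader might take any one of these ranges as a bound. Each depends on the assumed SD, adherence and ONT-negative share.

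**Conclusion.** The concern holds as a pre-specification fault whose consequence depends on the rule applied. Under the t-test, or the trigger without stent, power is lost almost entirely through stent. With all culture-negatives stopping at 24 hours, the loss is about 2 to 20 points at 0.05 and about 1.5 to 14 at the Primary Objective's p<0.1. With half stopping, it runs at 0.05 from about 1 point (weak stent link, SD 4) to about 40 (pilot link, SD 2). Under the screen the loss is mostly gone; what remains is a data-chosen model that may adjust for a post-randomisation variable, and the harm from that variable is not quantified here. The direction is firm. The size rests on a 42-patient pilot, instrumentation as a proxy for stent, and assumed SD and adherence. This should be changed, but it does not invalidate the trial.

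**What to change.** 1. Reconcile the five stratification factors of Section 2.1 General Design with the two of Sections 4.2 and 5.2, and state which were programmed.
2. Pre-specify the primary duration model as arm plus the programmed factors, fitted whatever the observed balance, with a robust standard error. Name these terms as the covariates meant in Section 2.2 Primary Objective. Keep the unadjusted t-test as a sensitivity analysis.
3. Remove the imbalance trigger, the p<0.15 screen and post-operative TPN from treatment comparisons. Keep the screen only for the exploratory SSI prediction model.
4. For the SSI treatment comparison, adjust for stent and operation type only. The pilot's 30-day rate gives about 0.214·140 = 30 events, too few for many terms.

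The cost is wording: stent and operation type are already collected for randomisation. The duration model gives up one or two degrees of freedom with two factors, and five or more if all five were programmed, which is still small with 140 patients.

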After sequencing data is gathered, samples will be destroyed. The data results from the ONT sequencing testing will be entered into EMR as a research clinic note for documentation and results will additionally be emailed to the medical providers on the care team. Decisions on antibiotic regimen will be made with the assistance of Surgical Clinical Pharmacy with changes in regimens as deemed appropriate based on standard cultures and ONT results, as described in Table 5. A negative ONT result will result in discontinuation of perioperative antibiotics after 24 hours while a positive ONT result will be used to guide early targeted antibiotic therapy (Table 5). With regards to early discontinuation of antibiotics, we are confident that this will not adversely impact patient care as our preliminary data demonstrated that ONT resulted in no false negative calls. However, as this is a new technology, SC will be performed alongside ONT, and if microbial growth is detected in the cultures, the clinician will have the option of reverting patient care to current standard of practice. This option will also be available in the event of treatment failure in patients with positive ONT results (Table 5).

Given that currently clinically available tests will be available to the care team with the additional ONT sequencing as supplemental data there will be minimal risk to subjects participating in this study.

Table 5 Incorporation of ONT results in clinical management decisions

ONT Result	Clinical management decision
A negative ONT result	Discontinue antibiotics after 24 hours of peri-operative coverage

A positive ONT result for a single pathogen typical of biliary or gastrointestinal flora	Adjust and/or narrow antibiotic therapy to cover single pathogen. If single pathogen deemed clinically insignificant (ie. lactobacillus), discontinue antibiotics after 24 hours of peri-operative coverage.
A positive ONT result for multiple pathogens	Adjust and/or narrow antibiotic therapy to cover all pathogens, excluding those deemed clinically insignificant. If all pathogens are considered clinically insignificant, discontinue antibiotics after 24 hours of peri-operative coverage.
A positive ONT result positive for rare or unexpected flora	Adjust and/or narrow antibiotic therapy to cover rare or unexpected flora, excluding those deemed clinically insignificant.

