ONT results different from SC	Adjust and/or narrow antibiotic therapy to cover pathogens found in ONT results, excluding those deemed clinically insignificant. SC results to only be considered in the event of treatment failure with antibiotic therapy targeted towards ONT results.

Databases Used

For the analysis of our endpoints, we are relying on sequence homology for two main tasks, mainly, (1) the identification of species and (2) identification of AMR phenotypes. For species identification, we use the refseq genome database (downloaded on 12/18/2020) with all data from the following higher order taxa groups included: human, protozoa, viral, bacterial, and fungal. For the identification of AMR phenotypes, we use the ResFinder database (downloaded on 06/04/2021, version 4.1) which contains the acquired chromosomal resistance genes, ensuring we know which species is carrying a given resistance gene. For plasmid AMR gene identification, we will use the PlasmidFinder-specific database (downloaded on 7.14.2021/version 2.0.1) and the CARD data (downloaded on 07/07/21, version CARD 2020). These databases undergo regular updates since they were first developed. To ensure the analysis remains consistent throughout the study, databases will not be updated for the duration of the study. In the unlikely event that we require a software/ database update in order to run these tools (compatibility issues with future institutionally required OS update, inability to restore databases from archives after computational disaster), we will validate any newer versions of the database and/or algorithms using the data and culture gold standards from our published study and recently collected data and will only proceed if we have comparable performance in accuracy for species and AMR identification.

Patient Follow-up and Safety Monitoring

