- Diabetes mellitus co-morbidity at time of surgery (clarifications needed for data collection)
- Cancer diagnosis
- ASA score at time of surgery
- Administration of chemotherapy prior to surgery (from what timepoint or date of last chemo?)
- Presence of biliary stent at time of surgery
- Blood loss during surgery
- Length of surgery (skin to skin, open to close?)
- Vascular reconstruction (arterial, venous) during surgery
- Closure technique
- Pancreatic leak risk score (when done? In record?)
- Surgical drains (what is needed)
- Post-op TPN

Variables with p-values less than 0.15 will be considered as potential candidates for a multivariable model. We will report odds ratios and 95% confidence interval. The area under the receiver operating characteristic (ROC) curve will be estimated as a measure of the ability of the model to discriminate between patients who had SSI within 90 days versus those who did not. An area under the ROC estimate of 0.7–0.8 will be regarded as acceptable, 0.8–0.9 will be regarded as excellent, and more than 0.9 will be regarded as outstanding.

We will also assess cost effectiveness of using ONT compared to SC. To achieve this, we will compare the cost to perform SC testing and ONT testing against costs associated with post-operative patient care. This will include the total cost to administer perioperative antibiotics, costs associated with length of hospital stay, and the costs associated with the need of additional procedures and tests associated with SSI (i.e. post-operative SC and antibiotic susceptibility testing, additional antibiotics, wound debridement, abdominal abscess drainage, CT scan, US scan).

For continuous variables, t-test will be performed and for binary variables chi-square or fisher's exact testing will be performed as appropriate. Additional analysis will be performed as necessary to determine differences in study arms. Should additional analysis beyond the scope of our abilities is necessary then a statistician will be employed.

Inpatient related costs associated with each intervention arm will be analyzed and compared with the assistance of the Robert D. and Patricia E. Kern Center for Science of Health Care in order to understand the economic impact of each intervention arm.

Handling of Missing Data

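### The duration analysis does not commit to adjusting for biliary stent, a randomisation factor that largely predicts course length, so power depends on a modelling choice left open until the data are seen

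*Combined protocol and SAP*

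**What the plan says.** Section 2.2 (Primary Objective) defines success as "Significantly reduced antibiotic regimen duration and use of broad-spectrum antibiotics, corrected for key co-variates", at p<0.1. It does not name the covariates. Section 5.3 lists duration among the primary outcomes.

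Section 6.2 states that "Duration of antibiotics, total number of different antibiotics, and broad-spectrum antibiotics vs narrow-spectrum antibiotics administered in the two arms will be compared". That sentence gives no model; later the section adds "For continuous variables, t-test will be performed". Adjustment has two routes:

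- Imbalance: "If there are any baseline imbalances in demographic or clinical variables between the two groups, we will perform the analysis" by regression on the unbalanced variables.
- Screening: a candidate list for the primary and secondary models, from which a variable with p<0.15 becomes a possible entry to a multivariable model. Stent is on the list. Operation type and bile-culture result are not.

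Stent is a randomisation factor in sections 2.1 (General Design), 4.2 and 5.2. Operation type is the other factor in 4.2 and 5.2; section 2.1 adds age, sex and ASA score.

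On course length, section 2.1 gives both arms the same rule: "If bile cultures are positive, antimicrobials will be continued for a complete 10-day course of antibiotics". Culture-negative controls get up to 5 days, and sequencing-negative (ONT-negative) patients in Arm 2 stop after 24 hours. Table 5, in the same section, is less uniform. It says "If all pathogens are considered clinically insignificant, discontinue antibiotics after 24 hours of peri-operative coverage", and where the two tests differ, "SC results to only be considered in the event of treatment failure with antibiotic therapy targeted towards ONT results". No course length is stated for Arm 2 patients who are ONT-positive but culture-negative.

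**The concern.** Planned duration is close to two-valued: 10 days with a positive culture, 5 or fewer without. In the pilot, stent (recorded there as biliary instrumentation) almost identifies which group a patient falls in. Stratified randomisation balances stent between arms, so the arm difference varies less from trial to trial than the raw spread of durations suggests. A two-sample t-test ignores this and uses the full spread, so its standard error is too large.

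The imbalance route makes this worse: the better the stratification works, the less likely it is to trigger adjustment for the factor that matters most. The screening route would very probably admit stent, but nothing commits the team to keep it. The trial is open (section 4.3), so an unblinded team could choose between analyses of quite different power after seeing the results. A real shortening could then be reported as no effect.

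**Working it through.** **The plan's own figure.** Section 6.1 gives 66 per arm for 54% against 77% positivity, alpha 0.05, power 80%. With p̄ = 0.655:

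n = [1.960·√(2·0.655·0.345) + 0.842·√(0.54·0.46 + 0.77·0.23)]² / 0.23² = (1.318 + 0.549)² / 0.0529 ≈ 66.

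This reproduces exactly, but it concerns detection rates. The plan gives no power for duration.

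**Inputs for duration.**

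- 54% culture-positive (6.1). If every culture-positive patient is also ONT-positive (no false negatives in the pilot, 2.1), 77 − 54 = 23% are ONT-positive/culture-negative and 23% are negative on both.
- Courses from 2.1: 10 days if culture-positive, 5 for culture-negative controls (the stated maximum), 1 for ONT-negative patients in Arm 2.
- Stent (Table 1): 22 of 22 instrumented patients were microbe-positive, 1 of 20 others. φ = (22·19 − 0·1)/√(22·20·23·19) = 0.953, so φ² = 0.91.
- Assumed, because not stated: within-group SD of 1, 2 or 3 days; ONT-positive/culture-negative course of 5 or 10 days, or the group empty; 1:1 allocation within stent strata.

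**Expected arm difference.** Control mean: 0.54·10 + 0.46·5 = 7.70 days.

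- ONT-positive/culture-negative get 5 days: Arm 2 = 5.40 + 0.23·1 + 0.23·5 = 6.78; difference −0.92.
- Group empty (section 1.1 reports full agreement when culture was negative): 0.46·(1 − 5) = −1.84.
- They get 10 days: Arm 2 = 5.40 + 0.23 + 2.30 = 7.93; difference +0.23, so Arm 2 is longer.

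**Why the t-test is conservative (no true effect, SD 2).** Culture status alone gives a variance of 0.54·0.46·5² = 6.21. The t-test uses SE = √(2·(6.21 + 4)/70) = 0.54. Within stent strata little of that variance is left. The unstented share is 1 − 0.54·22/23 = 0.4835, of whom (0.54/23)/0.4835 = 4.86% are culture-positive. The remaining variance is 0.4835·0.0486·0.9514·25 = 0.56. The true SD of the estimate is √(2·(0.56 + 4)/70) = 0.36. Rejection at nominal 10% needs |difference| > 1.656·0.54 = 0.894, which is 2.48 true SDs: about 1.3%. Simulation (5,000 runs) gives 0.1/1.3/4.1% at SD 1/2/3 for the t-test, and 10.3/10.6/10.0% with stent in the model.

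**Power, 5-day case, SD 2.** The simulated reported SE is 0.64 unadjusted, while the true SD is 0.41. Unadjusted: Φ((0.92 − 1.656·0.64)/0.41) = Φ(−0.34) ≈ 37%. Stent-adjusted (reported SE 0.41): Φ(0.92/0.41 − 1.656) = Φ(0.59) ≈ 72%.

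**Simulated power (%), 70 per arm, p<0.1 in the shorter direction, SD 1/2/3 days:**

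| ONT-positive/culture-negative course | Difference (days) | Unadjusted | Stent-adjusted |
|---|---|---|---|
| 5 days | −0.92 | 47.8/36.7/29.5 | 93.6/71.5/49.8 |
| 5 days, stent a weaker proxy (assumed 80% of culture-positives and 20% of culture-negatives stented) | −0.92 | 48.8/40.3/32.5 | 60.1/50.2/38.5 |
| 5 days, and an assumed 10% of culture-positive Arm 2 patients stop at 24 hours under Table 5 | −1.41 | 89.5/75.8/60.0 | 99.5/91.4/75.5 |
| Group empty | −1.84 | 99.6/94.9/83.1 | 100/99.6/94.9 |
| 10 days | +0.23 | all under 3 | all under 3 |

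Normal errors around a 1-day course produce some impossible negative durations. Flooring durations at 1 day lowers the 5-day case at SD 2 to about 24 to 27% against about 62%: lower power, same gap.

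**The case against.** The plan is not silent on adjustment. The success criterion itself demands correction for covariates, so on its face a bare t-test is not the success analysis. Stent is on the candidate list and passed the p<0.15 screen in every simulated run. This stands: a reader might infer that the trial has 37% power for duration, but that is only one reading of the plan, and perhaps the less likely one. What remains is that no covariate is named, passing the screen does not guarantee retention, and section 6.2 also offers the plain t-test.

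A reader might also infer that courses differ between arms only in culture-negative patients. The arm descriptions in section 2.1 support that, but Table 5 does not, and when cultures grow "the clinician will have the option of reverting patient care to current standard of practice". The point needs only that culture status largely sets course length.

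A third tempting step is to make final culture growth the primary covariate. At the pilot's proxy strength that adds only about 2 to 6 points over stent. Culture can take 24 days to finalise, whereas stent is a baseline variable, already stratified on and already listed. Requiring culture as the main covariate would be a preference.

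Finally, the trial is labelled a pilot and claims no power for duration. That limits the seriousness, but the adjustment costs nothing.

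**Conclusion.** The point holds as a loss of power and precision, together with an analysis choice left open. It is not bias: randomisation keeps the unadjusted contrast unbiased, and the unadjusted test errs on the conservative side, so nothing here supports a reading of inflated false positives from that test.

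The size depends on facts that the plan does not give. At SD 2 days, committing to stent adjustment gains about 35 points of power if ONT-positive/culture-negative patients get 5 days, about 5 if that group is empty, and nothing useful if they get 10 days. In that last case Arm 2 is expected to be longer, and no covariate can rescue the endpoint. The 5-day gain shrinks to about 10 points if stent is a much weaker proxy than in the pilot. All figures rest on an assumed SD, on treating pilot instrumentation as stent, and on simple stratified allocation. The claim concerns duration only. It is worth fixing because the criterion is primary and the change is nearly free.

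**What to change.** In section 6.2, replace the open comparison of duration with: the arm difference in antibiotic duration is estimated by linear regression on arm, biliary stent and operation type; these factors are always included, whatever the baseline balance or screening p-value; the p<0.1 criterion in section 2.2 applies to this estimate, which is reported with its 95% CI. If the longer list of stratification factors in section 2.1 governs, include those factors too.

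Adjustment for growth on the intraoperative bile culture, and the arm effect in culture-negative patients (about 0.46·70 = 32 per arm), may be prespecified as supportive analyses. It would also help to state the course length for ONT-positive/culture-negative patients, and whether the arm descriptions or Table 5 govern culture-positive patients in Arm 2.

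The cost is a few sentences. No new patients or data are needed: stent and operation type are recorded for randomisation, and section 5.3 already captures all culture results.
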